Rationale: We are not aware of RCTs comparing treatment entry and retention rates for jail-based methadone maintenance (with or without PN) compared to detoxification. However, a longitudinal evaluation from Rikers Island has shown better treatment entry rates post-release for inmates started on MM rather than provided with detoxification²² and MM has significantly higher treatment retention rates than methadone detoxification in non-incarcerated populations.⁷ Therefore, we hypothesize that participants assigned to IM with or without PN are more likely to enter and remain in community-based treatment, and associated superior treatment outcomes.

Hypothesis 1B: The IM+PN condition will have higher rates of treatment entry and longer retention, and concomitant lower rates of illicit opioid and cocaine use, meeting DSM-5 criteria for opioid and cocaine dependence, HIV risk behavior, criminal behavior, arrests, and days of incarceration than will the IM Alone condition.

Rationale: Reports on the rates of entry into community-based MM treatment of inmates started on MM in Rikers Island range from 14%²⁰ to 50%²² leaving considerable room for improvement. PN has been found to yield higher rates of treatment entry than no-PN in non-jail and non-prison samples of opioid-addicted adults.³³ We expect that PN, by reducing barriers to continued treatment in the community and re-engaging those who drop out over the first 3 months of MM, will result in the IM+PN condition having higher rates of treatment entry and longer retention in treatment, and associated superior treatment outcomes. [We are cognizant of the possibility that the effects may be attenuated at the 6-month and 12-month follow-up compared with the initial 3 month follow-up.]

AIM 2 To determine the relationship of gender to the relative effectiveness of treatment conditions.

Hypothesis 2A. Women in the IM+PN condition will have superior outcomes to men in the IM+PN condition in terms of (a)-(e), above; **Hypothesis 2B:** in contrast, women in the IM alone and methadone detoxification conditions will have poorer outcomes than men in the IM alone and methadone detoxification conditions.

Rationale: The few studies of reentry from incarceration that examined outcomes for opioid-dependent men and women started on MM have shown that women are less likely to enter and remain in treatment.²²

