However, the PN literature shows that women respond well to this intervention.^{116,117} Therefore, although we anticipate that women will have poorer outcomes than men in the IM alone and detoxification conditions, we hypothesize that women will respond better than men to IM+PN.

Analyses for Aims 1 and 2.

Intent-to-Treat Approach. All analyses will be conducted on available study-related data from all participants (based on their random assignment to treatment condition), regardless of whether or when they drop out of treatment.

Guiding Principle. Although the description of the statistical approach that follows is more in line with the language associated with a ‘traditional’ superiority trial, we endorse the “sensible formulation of the significance test” proposed by Jones and Tukey.¹¹⁸ They outline an approach to significance testing that focuses not on the rejection of a null hypothesis, but on determining whether the data favor a determination of superiority or inferiority. As part of their approach, they suggest reporting not only a test statistic and its associated probability value but also a confidence interval and an effect size related to the determination of any difference. It would be our intention in reporting our results to adhere to Jones and Tukey’s suggestions.

Outcome Variables. Outcome variables will be of three distinct types: 1) dichotomous variables (e.g., entry into treatment, illicit opioid and cocaine urine test results, meeting DSM-5 opioid and cocaine dependence criteria), assumed to follow a binomial distribution; 2) discrete random variables (e.g., number of days of heroin and cocaine use and criminal behavior in the past 30 days), assumed to follow a Poisson distribution; and, 3) continuous random variables (e.g., HIV Risk scale scores), assumed to follow a normal distribution. All distributional assumptions will be evaluated prior to the conduct of all analyses, and if such assumptions are not met, assumptions will be modified and statistical methods chosen accordingly, and/or outcome measures transformed appropriately. For example, it may be necessary to allow for under- or over-dispersion in the logistic and Poisson regression analyses; or a negative binomial model may be more appropriate for the count variables. [In the case of transforming an outcome variable, preference will be given to a transformation that permits clearer clinical interpretation of findings].

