Explanatory Variables. The predictor variables in all statistical models can be categorized as either Treatment Variables, Moderator Variables, or Control Variables.

Treatment Variables: There will be a single treatment variable with three conditions: Intervention Condition [IM+PN v. IM Alone v. Methadone Detoxification (ETAU)].

Moderator Variables: There will be a single moderator variable: Participant Gender.

Control Variables: Three additional predictor variables – participant age, prior methadone maintenance treatment (yes v. no), and self-reported cocaine use at baseline – will be included as “main effects” in all analyses in order to examine for potential differences in treatment outcome as a function of these three variables. (In the parent study: 56% had never previously been in MM treatment; and, self-reported cocaine use at baseline predicted lower treatment retention at 6 months).

Time: Finally, the “repeated factor” in the statistical analysis of all outcome variables measured repeatedly will be assessment Time point, which will allow for the evaluation of both *differential course and impact* of the interventions as a function of the “between-subjects” Treatment Condition factor. (For information regarding which outcome variables are measured at what assessment time points, see **Figure 1. Outcomes and Measures by Aim and Measures**, above).

Planned Contrasts: It is possible to construct two orthogonal, single-degree-of-freedom, planned contrasts that directly test **Hypothesis 1A** and **1B**, respectively. Contrast 1A will compare the two IM treatment conditions (IM+PN and IM Alone, pooled) to the Methadone Detoxification condition. Thus, this comparison directly addresses the question of the differential effectiveness of some form of IM treatment in comparison to a ‘minimally sufficient’ treatment-as-usual (methadone detoxification). Contrast 1B will compare the IM+PN condition to the IM alone condition. Hence, this comparison directly addresses the question of the relative

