effectiveness of the adding PN to IM treatment. Similarly, it is possible to construct two orthogonal, single-degree-of-freedom, planned contrasts that directly test **Hypothesis 2A** and **2B**, respectively. Contrast 2A will compare males and females in the IM+PN condition. Hence, this comparison directly addresses the question of the differential effectiveness of IM+PN treatment for males and females. Contrast 2B will compare males and females in the IM Alone and Methadone Detoxification conditions, pooled. Thus, this comparison directly addresses the question of the differential effectiveness of non-PN treatments for males and females. Given that both the course and impact of treatment are important to evaluate, planned contrasts can be examined both as each interacts with the “repeated factor” of Time (when there is a repeated factor), and as a “simple effect” at a given time point, in the event either Contrast X Time interaction effect proves to be significant.

AIM 3: To conduct a focused cost-effectiveness and cost-benefit study of the three treatment conditions

HYPOTHESIS 3a (Cost Hypothesis). IM alone will have greater treatment costs per person than detoxification. Furthermore, IM+PN will have greater treatment costs per person than IM alone.

HYPOTHESIS 3b (Cost-Effectiveness Hypothesis). IM+PN will yield better outcomes relative to the IM alone which in turn will yield better outcomes than detoxification in terms of higher rates of treatment entry and longer retention in treatment, and greater reductions in illicit opioid and cocaine use, decreased likelihood of meeting DSM-5 criteria for opioid and cocaine use disorders, decreased HIV risk behavior, and decreased criminal behavior, arrest, and incarceration. The better outcomes for IM+PN justify the greater costs of IM+PN compared to IM alone, making IM+PN cost effective compared to IM alone.

HYPOTHESIS 3c (Cost-Benefit Hypothesis). IM alone will yield greater economic benefit in terms of criminal activity, health care utilization, and employment in the 12-month post-release period relative to its costs relative to the detoxification condition. Furthermore, IM+PN will yield greater economic benefits than IM alone.

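### Aim 2 asks whether gender changes the relative effectiveness of the conditions, but the plan tests only women versus men within conditions and specifies no gender-by-condition contrast

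*Combined protocol and SAP*

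**What the plan says.** The protocol states Aim 2 as "To determine the relationship of gender to the relative effectiveness of treatment conditions". Under Explanatory Variables it says "There will be a single moderator variable: Participant Gender". Hypothesis 2A predicts that women will do better than men under IM+PN. Hypothesis 2B predicts the reverse elsewhere: "women in the IM alone and methadone detoxification conditions will have poorer outcomes than men in the IM alone and methadone detoxification conditions".

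The Planned Contrasts paragraph gives one contrast for each hypothesis:

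- **2A:** "Contrast 2A will compare males and females in the IM+PN condition". The plan's reading is that "this comparison directly addresses the question of the differential effectiveness of IM+PN treatment for males and females".
- **2B:** "Contrast 2B will compare males and females in the IM Alone and Methadone Detoxification conditions, pooled". The plan's reading is that "this comparison directly addresses the question of the differential effectiveness of non-PN treatments for males and females".

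The only interaction described for these contrasts is with Time. The Power section covers Contrasts 1A, 1B, 2A and 2B and nothing else. Nowhere does the plan write 2A minus 2B, gender by Contrast 1A or 1B, or an overall gender-by-condition test.

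**The concern.** Whether gender alters relative effectiveness is a question about a difference between conditions in the gender gap. A gender gap inside one condition, or inside two pooled, has no comparator condition. If women did worse than men by the same amount in all three arms, treatment would have nothing to do with it, yet 2A and 2B could both be significant and the stated reading would call each one differential effectiveness.

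The plan gives reason to expect such gaps. Its section on gender differences reports that women leaving jail were somewhat less likely than men to enter and stay in treatment, and Hypothesis 2B itself predicts poorer outcomes for women in both non-navigation arms. In the other direction, real moderation that falls short of a full crossover, such as navigation closing a deficit that women have elsewhere, has no prespecified test.

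**Working it through.** **The plan's own power figure.** The Power section gives .9 for a planned contrast by Time at f² = .048, N = 270, alpha .01. A noncentral F calculation gives .83 to .84 with 1 numerator df (two-sided) and .887 to .895 if the .01 is one-sided. Degrees of freedom and sidedness are not stated, so the figure can be neither confirmed nor called wrong. The point below does not depend on it, and the plan states no figure for a gender-by-condition contrast.

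**Algebra (no assumptions about effect size).** Let a be the women-minus-men difference in IM+PN, and b and c the same difference in IM alone and ETAU.

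- 2A = a; 2B = (b + c)/2; I = 2A − 2B; mean gap g = (a + b + c)/3 = (2A + 2×2B)/3.
- Hence 2A = g + 2I/3 and 2B = g − I/3.

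Both contrasts carry g in full. Only I is free of it.

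**Inputs for the illustration.**

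- 150 men and 150 women, 100 per arm, allocation 1:1:1 within gender (Participants, Project Timeline, Random Assignment): 50 per gender-by-arm cell, or 45 at N = 270.
- Alpha .01 (Power section); two-sided is assumed, so z = 2.576.
- Unit SD, continuous outcome, equal cells: assumed.
- Gap of 0.28 SD: the background on linkage to community treatment reports 5-month retention of 40% for men and 27% for women at Rikers, among those who entered treatment. 2·asin(√.40) − 2·asin(√.27) = 0.277. Applying this to every arm is an assumption. A 0.5 SD gap is shown for range.

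**Standard errors at 50 per cell.** 2A: √(2/50) = 0.200. 2B: √(2/100) = 0.141. 2A − 2B: √(.04 + .02) = 0.245.

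**1. Same gap in every arm, no moderation, outcome tested without Time.** The rejection probability is Φ(d/SE − 2.576), plus a negligible opposite tail.

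| Uniform gap | 2A | 2B | At least one | 2A − 2B |
|---|---|---|---|---|
| 0.28 SD, N = 300 | 12% | 27% | 1 − (.883)(.732) = 35% | 1% |
| 0.28 SD, N = 270 | 10% | 24% | 31% | 1% |
| 0.5 SD, N = 300 | 47% | 83% | 91% | 1% |

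An exact binomial check of 40% v. 27% gives 11.0% for 2A and 26.5% for 2B. With women worse by 0.28 SD, 2A comes out significantly in women's favour only 0.004% of the time. The hypothesised double crossover (2A favouring women, 2B favouring men) occurs at most 0.003% of the time under any uniform gap, and a crossover in either direction at most 0.005%.

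**2. The pattern of 2B significant and 2A not.**

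| Truth | 0.28 SD | 0.5 SD |
|---|---|---|
| Uniform gap (no moderation) | .268 × .883 = 24% | .831 × .530 = 44% |
| Navigation removes the deficit (moderation) | .268 × .99 = 27% | .831 × .99 = 82% |

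At 0.28 SD the pattern barely separates the two explanations.

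**3. Repeated outcomes.** A constant gap cancels in Contrast × Time, so rejection stays at 1%. A gender difference in change that is common to all arms does not cancel. Assume a 0.3 SD shift at every follow-up, compound symmetry and a k-df chi-square test with baseline plus k follow-ups. At correlation .5, 2A and 2B reject 14% and 35% (k = 2, as for the HIV risk battery), 13% and 33% (k = 3), and 12% and 32% (k = 4). Over correlations .3 to .7 the ranges are 8–27% and 20–61%.

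**Which outcomes fall where.** The Power section treats retention and arrest/incarceration as having no Time effect, and Figure 1 schedules treatment entry once, at 1 month. For these, a constant gap enters both contrasts. The other repeated outcomes fall under item 3.

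**The case against.** The strongest reply is that the contrasts test Hypotheses 2A and 2B exactly as worded, and that the opposite-direction pattern those hypotheses predict would itself establish moderation. Both are true, and a uniform gap almost never produces that pattern. The rejections in item 1 are also correct statements about which gender did better in those arms; they become errors only when read as an effect of treatment. But the plan gives that reading in so many words, and for each contrast separately.

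A second reply is that the plan endorses "reporting not only a test statistic and its associated probability value but also a confidence interval and an effect size", so 2A minus 2B could be worked out from what is reported, and clearly separated intervals would point to a difference. This stands as far as it goes: the data are not lacking. Separation of intervals is not a test the plan states, however, and it is weak. If navigation removed a 0.5 SD deficit, the two 99% intervals would separate about 6% of the time.

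A third is that calling gender a moderator implies an interaction term. It may, but a term in a model is not a prespecified contrast.

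A fourth is that retention, measured as enrolment at 3, 6 and 12 months in Figure 1, might be modelled with Time, in which case a constant gap would cancel. The Power section says otherwise for that outcome, and a gender difference in change common to all arms would remain.

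Finally, the gap sizes are assumptions. The percentages illustrate the defect; the algebra establishes it.

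**Conclusion.** The concern holds and should be fixed. The contrasts match the hypotheses, but neither contrast alone answers Aim 2, and the statement that each directly addresses differential effectiveness is wrong. Short of a double crossover, the plan has no prespecified test of moderation. The structural conclusion rests on no numerical assumption. Its size does: equal cells, unit SD, two-sided alpha .01 and an assumed uniform gap between 0.28 and 0.5 SD, giving rejection by 2A of 12% to 47% and by 2B of 27% to 83% where gender modifies nothing.

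**What to change.** - Prespecify 2A minus 2B as the Aim 2 test of moderation: (women minus men in IM+PN) minus (women minus men in IM alone and ETAU pooled), by Time where the outcome is repeated.
- Report it with a confidence interval, on the model's link scale for binary and count outcomes. Absolute differences alongside would help, because a uniform gap depends on the scale: 13 points is 0.53 in log-odds at 50% v. 37% and 1.20 at 20% v. 7%.
- Keep 2A and 2B as within-condition gender differences for Hypotheses 2A and 2B, and reword Planned Contrasts so that neither alone is called a test of differential effectiveness.
- Optionally add gender by Contrast 1A and gender by Contrast 1B as secondary, since pooling IM alone with ETAU cannot show modification between those two.
- State the precision of the interaction in the Power section.

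The cost is wording and one contrast in the same model and data. The drawback is modest power. At alpha .01 and 80% power the detectable difference is (2.576 + 0.842) × 0.245 = 0.84 SD at N = 300, and 0.88 SD at N = 270 (SE 0.258). If navigation only removes a 0.5 SD deficit, power is about 30% (26% at N = 270); for 0.28 SD it is 7%. The secondary contrasts have SEs of 0.245 SD (gender by 1A) and 0.283 SD (gender by 1B), with detectable differences of 0.84 and 0.97 SD. The interval will therefore tell the reader more than the test.

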Substance Abuse Services Cost Analysis Program (SASCAP): Costs for each of the study conditions will be estimated using an activity-based costing approach which will allow cost estimation at the service level for study participants. To collect resource use and cost data necessary for activity-based costing, we will modify the SASCAP⁹⁰ to collect resource use and cost data for each condition necessary for activity-based costing. The SASCAP consists of a provider questionnaire administered once during the intervention phase to collect activity-level resource use and cost data for provider staff and nonlabor resources such as contracted services, building space, supplies and materials, and other miscellaneous resources (e.g., utilities). The SASCAP method reliably estimates the costs of specific treatment activities and the total cost per patient, and the investigators [name] and [name] have applied this micro-costing approach in other treatment studies.^{66,89,114,115} If a significant number of participants transition from the initial MMP to another MMP or buprenorphine treatment, costs for these treatments will also be determined.

AIM 1. To determine the relative effectiveness of IM+PN v. IM alone v. brief methadone detoxification (enhanced treatment-as-usual [ETAU]) for opioid-dependent detainees at 1, 3, 6, and 12 months post-release in terms of: (a) post-release treatment entry and retention; (b) illicit opioid and cocaine use; (c) meeting DSM-5 criteria of opioid and cocaine dependence; (d) HIV-risk behavior; and (e) criminal behavior, arrest, and days of incarceration.

Hypothesis 1A: The IM+PN and IM Alone conditions will have higher rates of treatment entry and longer retention, and concomitant lower rates of illicit opioid and cocaine use and of meeting DSM-5 criteria for opioid and cocaine use disorders, HIV risk behavior, criminal behavior, arrests, and days of incarcerations than will the Methadone Detoxification [ETAU] condition.

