Assuming $\alpha=.01$ and $N=300$, the resulting SAS GLIMMIX power estimates ($1 - \beta$) for the four planned contrasts X Time (see *Planned Contrasts*, above; for retained in treatment and arrest and incarceration, the effect of interest was necessarily the four planned contrasts themselves, as there was no Time effect for this outcome) associated with **Hypothesis 1A, 1B, 2A, and 2B** exceeded .81 in all cases, assuming “small” differences associated with each such effect, and even assuming an unstructured covariance matrix. For the set correlation approach, and in this case assuming $N=270$ due to attrition (see *Follow-up and Attrition*, above) in order to remain conservative, an effect size in the population associated with a Planned Contrast X Time for **Hypothesis 1A, 1B, 2A, and 2B** of $f^2=.048$ (.094 for retained in treatment and arrest and incarceration) would yield a power of .9 for that effect. [All 4 Planned Contrasts X Time for **Hypothesis 1A, 1B, 2A, and 2B** have the same degrees of freedom, so yield a common effect size.] The effect size involving the Time effect falls in the “small” range, while the effect size that does not include a Time effect falls in the “small-to-medium” range, with $f^2=.02$ considered a “small” effect and $f^2 = .15$ a “medium” effect.¹²¹

9. Process Evaluation.

9.a. Need for Process Data: Due to the key role of PN in this study for overcoming barriers associated with community re-entry (**Aim 1**), particularly for women (**Aim 2**), we will conduct a qualitative process evaluation that will examine PN experiences in detail.

9.b. Qualitative Sample Selection: Using purposive sampling, a subset of 32 participants (16 IM+PN and 16 IM alone) will be selected to complete semi-structured qualitative interviews. Participant selection will emphasize heterogeneity in order to examine the views and experiences from as diverse a sub-sample as possible and will include an equal number of men and women from each condition. The proposed sample size will ensure that saturation is likely to be achieved (i.e., bringing new participants into the study until the data set is complete, as indicated by data replication or redundancy) and should allow for the extraction of thick, rich data

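### For repeated outcomes the plan spells out and powers only Contrast X Time, and gates visit-level effects on it, although Hypotheses 1A and 1B concern post-release levels

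*Combined protocol and SAP*

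**What the plan says.** All references are to the combined protocol and SAP.

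- **Hypotheses 1A and 1B** are about levels. After entry and retention, 1A predicts "concomitant lower rates of illicit opioid and cocaine use and of meeting DSM-5 criteria for opioid and cocaine use disorders", and 1B predicts the same pattern for navigation added to interim methadone.
- **Planned Contrasts** (under Analyses for Aims 1 and 2) opens with the statement "It is possible to construct two orthogonal, single-degree-of-freedom, planned contrasts that directly test", said first of 1A and 1B and then, in like words, of 2A and 2B (for instance, "Contrast 2A will compare males and females in the IM+PN condition"). On their use it starts from this reason: "Given that both the course and impact of treatment are important to evaluate". It then offers, in permissive terms, two routes for outcomes with a repeated factor. One is the interaction of each contrast with Time, and the other is a comparison at a single visit. The second route applies only "in the event either Contrast X Time interaction effect proves to be significant".
- **Power** refers to "an effect size in the population associated with a Planned Contrast X Time". The contrast itself is powered only for retention and for arrest and incarceration, where "the effect of interest was necessarily the four planned contrasts themselves, as there was no Time effect for this outcome".
- **Figure 1** lists DSM-5 criteria at baseline and at 3, 6 and 12 months, and most other Aim 1 outcomes at baseline and up to four follow-ups. **Section 3.a** requires opioid use disorder for entry. **Outcome Variables** makes meeting the DSM-5 criteria a dichotomous outcome.

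**The concern.** A Contrast X Time test asks whether a difference between conditions changes across visits. It does not ask whether a difference exists. With three or more time points it has several degrees of freedom and gives no direction, although the Guiding Principle asks for a determination of superiority or inferiority. The 1-df contrast that the plan calls direct has no stated role for repeated outcomes unless the interaction is significant, and then only visit by visit.

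If the wording is followed as spelled out, a treatment that lowers use disorder by the same amount at every follow-up could be passed over because its effect is stable. The stated power also belongs to a different test from the one the hypotheses call for. Leaving the deciding test open allows it to be chosen after the data are seen.

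The scope is limited to outcomes with a repeated Time factor. Treatment entry (one visit), arrest and incarceration, and retention as the Power section describes it are not affected.

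**Working it through.** **The plan's own figures.** Power gives f²=.048 for Contrast X Time (.094 without Time) for power .9 at alpha .01 and N=270. These cannot be rebuilt, because the degrees of freedom are not given. With noncentral F, power .9 needs f²=.056 with 1 numerator df, .079 with 4 and .097 with 8. The point here does not depend on them. It depends on which effect was powered.

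**Inputs.** From the documents: N=270 (Power) and equal arms (Project Timeline), so 90 per arm, giving 180 v 90 for 1A and 90 v 90 for 1B. Alpha .01 is the power assumption; no analysis level is stated. Assumed: all rates, effects and within-person correlations ρ=.3/.5/.7. Results separated by slashes follow that order of ρ.

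**1. DSM-5 opioid use disorder, steady 40% v 60% at 3, 6 and 12 months.** The log-odds difference is ln(.4/.6) − ln(.6/.4) = −.811 at every visit.

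- *Contrast X Time.* Differences between visits are zero, so noncentrality is 0 and power equals alpha, .01. A baseline at which everyone is positive adds no information on the log-odds scale.
- *Averaged contrast, 1A.* The one-visit variance is 1/(180×.24) + 1/(90×.24) = .0694. Averaging three visits multiplies it by (1+2ρ)/3, giving .0370/.0463/.0556. Noncentrality is .811² divided by these: 17.8/14.2/11.8. Power is .95/.88/.81.
- *Averaged contrast, 1B.* The variance is 2/(90×.24) = .0926, so noncentrality is 13.3/10.7/8.9. Power is .86/.75/.66.

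**2. The gate.** If a significant interaction for either contrast opens the visit-level tests, the chance under a steady effect is 1 − (1−.01)² = .0199. Simulation of three arms of 90 (40/40/60%, 20,000 runs per correlation) gave .018 to .020. At alpha .05 the formula gives .0975.

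**3. Baseline not quite all positive.** With baseline as a fourth level of Time (correlation 0 or .1 with follow-up, 3-df interaction), interaction power is .03 (1A) and .02 (1B) at 98% positive, and .05–.06 and .04 at 95%. The result does not need an exact ceiling.

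**4. Fading benefit (comparator 60% throughout).**

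| Treated at 3/6/12 months | Contrast | Interaction | Averaged |
|---|---|---|---|
| 35/40/45% | 1A | .07/.11/.22 | .95/.89/.81 |
| 35/40/45% | 1B | .05/.08/.15 | .86/.76/.66 |
| 35/45/55% | 1A | .41/.59/.87 | .73/.61/.51 |
| 35/45/55% | 1B | .28/.43/.72 | .57/.46/.37 |
| 30/50/58% | 1A | .83/.95/1.00 | .66/.54/.45 |
| 30/50/58% | 1B | .66/.84/.98 | .51/.40/.32 |

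The better test depends on the trajectory.

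**5. Continuous outcome, baseline plus four visits, constant d=.3 after release, compound symmetry.** Let k = n₁n₂/(n₁+n₂), which is 60 for 1A and 45 for 1B.

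- *Interaction with baseline as a level (4 df).* The mean effect over five time points is .24, and the sum of squared deviations is .24² + 4×.06² = .072. Noncentrality for 1A is 60×.072/(1−ρ) = 6.2/8.6/14.4. Power is .26/.41/.71 (1B: .17/.27/.53).
- *Baseline-adjusted average (1 df).* Noncentrality for 1A is 60×.09/[(1+3ρ)/4 − ρ²] = 5.4/.385, 5.4/.375, 5.4/.285 = 14.0/14.4/18.9. Power is .88/.89/.96 (1B: .75/.76/.88).
- *Follow-up visits only.* Interaction power is again .01.

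**6. Gender contrasts, steady 40% v 60%.** With 150 men and 150 women, equal allocation within gender and 10% attrition, 2A is 45 v 45 and 2B is 90 v 90. The averaged contrast has .50/.39/.32 (2A) and .86/.75/.66 (2B), against .01 for the interaction.

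**The case against.** The strongest reply is that baseline is meant to be a level of Time. The Time paragraph points to Figure 1, which marks baseline for most outcomes. Contrast X Time would then test differential change from baseline, which fits wording elsewhere about changes and reductions, and it would respond to a steady post-release benefit. At d=.4 its power runs from .54 to .96 (1A) and .38 to .87 (1B) as ρ rises from .3 to .7. This is a natural reading, though the plan never states it. It is right that the plan is not blind to steady effects on outcomes that vary at baseline. At high correlation the interaction even beats an average without baseline adjustment (1B, d=.4, ρ=.7: .87 v .68). It does not beat the baseline-adjusted average in step 5, and for opioid use disorder it does not help.

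Other points also stand in part:

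- The verb introducing the two routes is permissive. The contrasts are defined without reference to Time, and a mixed model can supply the average. The averaged contrast is therefore unstated, not forbidden.
- Either may refer to each contrast's own interaction. The gate then opens at .01 instead of .0199.
- The Rationale for 1B allows for attenuation, and section 6.c limits navigation to three months, so a fade that favours the interaction is plausible.
- The power .01 result needs a benefit that is steady on the log-odds scale. The mild-fade rows show low interaction power without that exact condition.
- Confidence intervals and effect sizes are to be reported, and no document names DSM-5 opioid use disorder as primary. This limits the stakes.

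**Conclusion.** The concern holds. For repeated outcomes, the plan neither names nor powers the 1-df level test that matches 1A and 1B, and as worded it makes visit-level comparisons depend on a test of change. Under a steady 40% v 60% on DSM-5 opioid use disorder, that test has power equal to alpha (.01), against .81 to .95 (1A) and .66 to .86 (1B) for the averaged contrast. For a continuous outcome with d=.3 and baseline in the model, the loss is smaller but present at every correlation tried. These sizes rest on assumed rates, effects and correlations, N=270 and alpha .01, and a strong fade reverses the ranking. This should be fixed, but it is a gap to close and does not invalidate the design.

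**What to change.** 1. State that for each repeated outcome, contrasts 1A, 1B, 2A and 2B are each tested as a 1-df contrast averaged over the post-release visits, whatever Contrast X Time shows. Give the visit weights (equal weights were used above).
2. Say how baseline enters: as a covariate where it varies, and omitted for DSM-5 opioid use disorder. Gender is not randomised, so say whether 2A and 2B are baseline-adjusted.
3. Keep Contrast X Time as the test of course.
4. Report visit-level estimates with confidence intervals, ungated and descriptive. If they are tested, state a multiplicity adjustment, such as Bonferroni over visits.
5. State the analysis alpha and the power of the averaged contrast.
6. Separately, reconcile the Power section's statement that retention has no Time effect with Figure 1, which lists enrolment at 3, 6 and 12 months. If retention is a single derived measure, define it.

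The cost is wording and a new power statement. The downside is lower power than the interaction when a benefit fades and correlation is high: with 35/45/55% at ρ=.7, .51 v .87 (1A) and .37 v .72 (1B), and with the sharp fade the average is behind at all three correlations. Items 3 and 4 cover this. In the 35/45/55% case the 3-month contrast alone has power .90 (1A) and .77 (1B), or .82 and .65 with Bonferroni over three visits.
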